3.1.2 Primary and secondary outcomes

[figure not shown]
Primary and secondary outcomes are presented in in Table 3. Outcomes will be assessed during initial care (the date of enrollment to 14 days) and follow-up (30 days after initial care) unless otherwise specified.

Table 3. Primary and secondary outcomes

Measure	Description
Hospital admission rate at initial episode of care	The rate of initial hospitalization for the treatment of ABSSSI
Total admitted hospital days during initial care and follow up	Includes days during the initial hospitalization (for those initially hospitalized) and all other hospitalizations
Infection-related total admitted hospital days during initial care and follow up	Includes days during the initial hospitalization (for those initially hospitalized) and all other infection-related hospitalizations
ED length of stay at initial episode of care (time from triage to release from ED)	Time spent in ED in hours from triage to release (either admitted to the hospital, admitted to observation, or released to home)
Infection-related major surgical interventions that required operating room time during initial care and follow up	Number of major unexpected surgeries
	Number of major expected surgeries
	Number of all major surgical interventions unexpected or expected
Infection-related hospitalizations during initial care and follow up	Number of infection-related hospitalizations

Measure	Description
Infection-related hospitalizations during initial care and follow-up that resulted in admission to Intensive Care Unit (ICU)	Number of infection-related hospitalizations resulting in admission to the ICU.
All cause hospitalizations in the 30 days post discharge from the hospital or release from the ED	Number of all hospitalizations for subjects discharged from the ED and re-hospitalizations for subjects who had an initial hospital admission
Infection-related ED visits during initial care and follow up	Number of unexpected visits to ED
	Number of expected visits to ED
	All visits (unexpected and expected) to ED
Infection-related outpatient healthcare visits (e.g., physicians' office visits, ED visits, infusion center visits, home health visits) during initial care and follow up	Unexpected visits, by site (e.g., physicians' office visits, ED visits, infusion center visits, home health visits)
	Expected visits, by site (e.g., physicians' office visits, ED visits, infusion center visits, home health visits)
	All visits (unexpected and expected), by site (e.g., physicians' office visits, ED visits, infusion center visits, home health visits)
Use of PICC line or central line to administer antibiotic therapy during initial care and follow up	PICC line or central line placement for antibiotic therapy
Infection-related healthcare visits (e.g., hospitalizations, ED visits, other outpatient visits) due to PICC line or central line used	Unexpected visits due to PICC line (i.e. complications)
	Expected visits due to PICC line (i.e. initial placement, monitoring of PICC line)

Measure	Description
to administer antibiotic therapy during initial care and follow up	All visits due to PICC line (both unexpected and expected visits)
Serious adverse events (SAEs) during initial care and follow-up	All SAEs as defined in Section 5 Safety assessments
Patient satisfaction with care (subject reported)	Patient satisfaction with care (Subject-reported, Section 11.2- questionnaire similar to the final implemented version)
Patient work and productivity loss (subject reported)	Number of days with lost/reduced productivity during follow-up, as measured through Work Productivity and Activity Impairment Questionnaire (Section 11.4) ³⁰
Patient Health-Related Quality of Life (HRQoL) (subject reported)	Health-related quality of life (subject reported), as measured through the Medical Outcomes Study Short Form-12 (SF-12), with acute recall (1 week recall) (Section 11.5) ³¹

[figure not shown]
3.2 Data collection

Information on baseline characteristics, outcomes, and other measures will be collected following subject enrollment in the study and will be based on the medical record and CRFs that will be developed exclusively for use in this study.

Data collection will involve the use of the CRO's electronic data capture (EDC) system through use of CRFs, to which only authorized personnel will have access. Subject's data are to be entered into the EDC system by the investigator or designee using their assigned EDC user account. After data entry into the EDC system by the investigator or designee, a combination of manual and programmatic edit checks will be used to review the data for completeness, logic, and adherence to study protocol. As a result of these edits checks, data monitoring, and reviews, queries may be electronically issued to the site and should be answered electronically via the EDC system.

3.2.1 Data collection schedule

Table 5 describes expected follow-up. Follow-up visits will be scheduled for 24 hours after enrollment (post-period only), between 48-72 hours after enrollment (post-period only), 14 days after enrollment (both periods), and 44 days after enrollment (both periods). The follow-up visits during the post-period include a telephone call at 24 hours and a limited physical visit at 48-72 hours. However, for subjects unable to be seen back at the site, a telephone interview will suffice at 48-72 hours. Research data will be collected through follow-up visits at 14 days (telephone call can occur between 14 and 21 days from enrollment) and at 44 days (telephone call can occur between 44 and 51 days from enrollment), through a telephone interview of the subject in both the pre- and post-periods. Additionally, electronic medical chart data will be reviewed at the 14 day and 44 day time points from enrollment. Any additional visits to the visit schedule below will be at the discretion of the subject and treating physician.

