3.2.2 Patient Diary Aid

Patients will be provided with a bound, paper diary to record specific information about their health status on days in which they have an interaction with a health care provider. The diary is intended only as an aid to help patients remember details about health care appointments, medications, and medical tests. The diary will not be collected by or returned to study staff.

4 Safety assessments

At each visit, subjects are to be queried regarding any adverse events (AEs) or serious adverse events (SAEs) that have occurred since the previous visit. Subjects will be asked to volunteer information with a nonleading question such as, “How do you feel since your last visit?” Study site personnel will record all pertinent information in the subject’s CRF. All AEs will be recorded on the appropriate AE reporting page of the subject’s CRF whether or not they are considered causally related to the study drug (any antibiotic given for ABSSSI from enrollment, including the pre-period).

For every AE, the investigator will:

- Provide an assessment of the seriousness of the event (i.e., is it an SAE?), as well as the severity and causal relationship
- Document all actions taken with regard to the study drug
- Detail any other treatment measures taken for the AE
- Document the outcome of the AE

In addition, subjects will be reminded, as described in the ICF to notify site personnel of any AEs occurring from the time the subject signed the ICF until the final follow-up visit. Any AEs that are ongoing at the time of the final protocol-defined study visit will be followed until the condition returns to pre-study status, has resolved or stabilized, or can be explained as being unrelated to the study drug. If a follow-up visit is deemed necessary for appropriate safety surveillance, it will take place within 30 days of the final protocol-defined study visit.

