4.4 Secondary Outcomes

[figure not shown]
[figure not shown]
Secondary outcomes will be assessed during initial care (the date of enrollment to day 14) and/or follow-up (30 days after initial care), and include:

[figure not shown]
[figure not shown]
Measure	Definition	Period of Assessment
Total admitted hospital days	Total LOS during the 44 days of the study (including initial hospitalization)	Initial care and follow-up
Infection-related total admitted hospital days	Total LOS of all infection related hospitalizations during the 44 days of the study (including initial hospitalization)	Initial care and follow-up
ED LOS	Time spent in ED in hours from triage to release (either admitted to the hospital, admitted to observation, or released to home)	Initial episode of care
Infection-related major surgical interventions that required operating room time	Number of all, unexpected and expected infection-related major surgical interventions that required operating room time	Initial care and follow-up
Infection-related hospitalizations	Number of infection-related hospitalizations	Initial care and follow-up
Infection-related hospitalizations that resulted in admission to intensive care unit (ICU)	Number of infection-related hospitalizations resulting in admission to the ICU.	Initial care and follow-up
All cause hospitalizations in the 30 days following discharge from the initial hospitalization or release from the initial ED visit (if not hospitalized)	Number of all hospitalizations for patients discharged from the ED and re-hospitalizations for patients who had an initial hospital admission	Overall, including Initial care and follow-up
Infection-related ED visits	Number of all, unexpected and expected infection-related ED visits	Initial care and follow-up

Measure	Definition	Period of Assessment
Infection-related outpatient healthcare visits (e.g., physicians' office visits, ED visits, infusion center visits, home health visits)	Number of all, unexpected and expected infection-related outpatient healthcare visits, generated for all patients and repeated by site.	Initial care and follow-up
Use of PICC line or central line to administer antibiotic therapy	Number of PICC line or central line placement for antibiotic therapy	Initial care and follow-up

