4.7 Safety

At each visit, patients will be queried regarding adverse events (AEs) and SAEs, and medication errors that occurred since the previous visit. Specifically, patients will be asked to volunteer information with a non-leading question

such as, "How do you feel since your last visit?" Study site personnel will record all pertinent information in the patient's case report form (CRF), as described in details in the protocol.

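### Two extra scheduled contacts in the post-period only make early adverse-event ascertainment unequal, and the plan does not say whether the 48-72 h visit counts as outpatient use or cost.

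*Protocol*

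**What the plan says.** Protocol Section 3.2.1 sets the contact schedule: "Follow-up visits will be scheduled for 24 hours after enrollment (post-period only), between 48-72 hours after enrollment (post-period only", followed by "14 days after enrollment (both periods), and 44 days after enrollment (both periods". The post-period contacts "include a telephone call at 24 hours and a limited physical visit at 48-72 hours", with an exception: "for subjects unable to be seen back at the site, a telephone interview will suffice at 48-72 hours". The day 14 and day 44 contacts are telephone interviews in both periods, each backed by review of the electronic chart. SAP Section 3.0 gives the same schedule.

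The opening of the Protocol's Safety assessments chapter ties adverse-event questioning to these contacts: "At each visit, subjects are to be queried regarding any adverse events (AEs) or serious adverse events (SAEs) that have occurred since the previous visit". SAP Section 4.7 repeats the rule: "At each visit, patients will be queried regarding adverse events (AEs) and SAEs". SAP Section 6.2.10 then summarises all adverse events by period.

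For outpatient use, SAP Section 4.4 defines the measure as "Number of all, unexpected and expected infection-related outpatient healthcare visits". SAP Section 6.2.5.2 tabulates none, any, 1, 2 and 3 or more visits by period, for all, expected and unexpected visits. SAP Section 6.2.12 includes healthcare visits among the unit costs.

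**The concern.** The secondary objectives are to estimate differences between periods. A difference in how often patients are asked, or in how many visits the protocol itself creates, enters those estimates whether or not a test is attached.

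Two mechanisms need to be kept apart. The first is ascertainment: a post-period patient is asked about adverse events at 24 h and again at 48-72 h, while a pre-period patient is first asked at 14 to 21 days. Vital signs at 48-72 h (SAP Section 6.2.8) and follow-up laboratory results (SAP Section 6.2.11) are also post-period only, and Protocol Section 4.1 allows an abnormal laboratory finding to be an adverse event. The second is counting: a scheduled study visit about the infection could be entered as an expected outpatient visit and costed.

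Both would tend to raise post-period figures, that is, to count against the new pathway. Lower outpatient use is one of the benefits hoped for in Protocol Section 1.2. The rationale in Protocol Section 2.3.4 aims at similar opportunity to collect outcomes, but it equalises only the 14 + 30 day window, not the number of contacts within it.

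**Working it through.** The plan states no figure on this point, so there is none to reproduce.

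**Scheduled contacts after enrollment** (Protocol Section 3.2.1)

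| | Pre | Post |
|---|---|---|
| 24 h call | 0 | 1 |
| 48-72 h visit (or telephone) | 0 | 1 |
| Day 14 telephone | 1 | 1 |
| Day 44 telephone | 1 | 1 |
| Total | 2 | 4 |
| Before day 14 | 0 | 2 |
| Physical | 0 | up to 1 |

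**Adverse events: illustration with no true difference.** Let *base* be the share of events captured by the day 14 and day 44 contacts plus the chart, *f* the share early enough for the extra contacts to find, and *q* the extra capture per added contact. Then post-period capture = base + (1 - base) × f × (1 - (1 - q)²), and pre-period capture = base. All three inputs are assumptions: base 0.6 to 0.9, f 0.6, q 0.2 to 0.4.

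- base 0.6, q 0.4: 0.6 + 0.4 × 0.6 × 0.64 = 0.754; ratio 0.754 / 0.6 = 1.26. With a true rate of 20%, 12.0% would be recorded pre and 15.1% post.
- base 0.9, q 0.2: 0.9 + 0.1 × 0.6 × 0.36 = 0.922; ratio 0.922 / 0.9 = 1.02.

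The recorded proportion is therefore 1.02 to 1.26 times higher post-period over this range. For serious events captured mainly from the chart, base is near the top of the range and the ratio is close to 1.

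**Outpatient visits, if the 48-72 h visit is counted.** There are 161 patients per period (SAP Section 3.0).

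- Ceiling: 161 × 1 = 161 visits, against 0 pre-period.
- Removing inpatients: at the planning rate of 23% admitted post-period (Protocol Section 5.3), 0.23 × 161 is about 37. If all are still in hospital at 48-72 h (assumption), 161 - 37 = 124 remain.
- Telephone substitution: if half of those 124 attend in person (assumption), 62 visits remain.
- Effect on the row for any visit: observed = p + (1 - p) × a, where p is the true proportion and a the share attending in person, taken as independent of other visits. With p = 50% and a = 50%, 0.50 + 0.50 × 0.50 = 75%.

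**Effect of an onset split.** After 72 h the scheduled contacts still to come are day 14 and day 44 in both periods: 2 against 2. The difference of 2 against 0 is confined to the early stratum.

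**The case against.** The strongest reply is that little hangs on this. The primary outcome, admission at the initial episode, does not depend on these contacts. SAP Section 6.2.5.2 states that the visit and serious-adverse-event outcomes will have no formal testing, and SAP Section 6.2 calls any secondary testing exploratory. That stands, and it limits the point to descriptive estimates.

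Scheduled questioning is also not the only source of adverse events. Both periods have chart review at days 14 and 44 and ongoing reporting by patients (SAP Section 6.2.10). The plan's own rates (38% admitted pre, 23% post) put more pre-period patients under early inpatient observation. This stands in part: it protects serious events well and mild or transient ones much less. A reader might infer that the serious-adverse-event comparison is materially biased. The documents do not support that, because most events meeting the definition in Protocol Section 4.4 would reach the chart in either period.

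A reader might also infer that the 48-72 h visit is in fact counted. Nothing available says so. Protocol Table 5, SAP Appendix A and SAP Section 4.6 (to which the cost section refers) are not in the public text, and a rule could be there. Unexpected visits are tabulated separately and should not be inflated by a scheduled visit. It could be argued that the visit is part of the pathway and ought to count. However, Protocol Section 1.1.5 defines the pathway by patient identification and dalbavancin, and does not name this visit. If the sponsor sees it as care, the SAP should say so.

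A tempting remedy is to compare only events detected at days 14 and 44. That would be wrong. Questions cover the time since the previous visit, so early pre-period events would be kept while early post-period events already reported at 24 h or 48-72 h would drop out. The adverse-event listing in SAP Section 6.2.10 also shows no field for the detecting contact.

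**Conclusion.** The point holds in limited form. Scheduled contacts are 4 against 2, and 2 against 0 before day 14, with no visible allowance in the analysis. Early, mild or transient adverse events are likely to be recorded more completely post-period. The ratio of 1.02 to 1.26 only illustrates the scale and rests wholly on assumed inputs. Serious adverse events are largely protected.

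For outpatient visits and costs, the point is an unsettled counting rule rather than a demonstrated bias. If the visit is counted, the built-in excess is at most one per post-period patient. It is about 124 visits in all if the planned 23% are admitted and still in hospital, and fewer again with telephone substitution. No claim about type I error or the primary result follows.

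**What to change.** In the SAP, before the data are tabulated:

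- **Adverse events.** Keep the full AE and SAE tables. Add one pre/post summary split by event onset: up to 72 h after enrollment, and later. Use the same fixed cut in both periods, because the pre-period has no contact to define it. Note under the table that scheduled questioning is equal for the later stratum only. SAP Section 6.2.10 lists a date for each event; confirm that it is the onset date, and give missing onset dates their own row. Do not restrict the comparison to events detected at days 14 and 44.
- **Outpatient visits and costs.** State whether the protocol-scheduled 48-72 h visit counts. Report it on its own row, and show outpatient-visit counts and total costs with and without it.

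The cost is a few extra table rows. Conduct and the primary analysis do not change. No new data should be needed, provided that onset date and visit type are recorded.

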3.2.2 Patient Diary Aid

Patients will be provided with a bound, paper diary to record specific information about their health status on days in which they have an interaction with a health care provider. The diary is intended only as an aid to help patients remember details about health care appointments, medications, and medical tests. The diary will not be collected by or returned to study staff.

4 Safety assessments

At each visit, subjects are to be queried regarding any adverse events (AEs) or serious adverse events (SAEs) that have occurred since the previous visit. Subjects will be asked to volunteer information with a nonleading question such as, “How do you feel since your last visit?” Study site personnel will record all pertinent information in the subject’s CRF. All AEs will be recorded on the appropriate AE reporting page of the subject’s CRF whether or not they are considered causally related to the study drug (any antibiotic given for ABSSSI from enrollment, including the pre-period).

For every AE, the investigator will:

- Provide an assessment of the seriousness of the event (i.e., is it an SAE?), as well as the severity and causal relationship
- Document all actions taken with regard to the study drug
- Detail any other treatment measures taken for the AE
- Document the outcome of the AE

In addition, subjects will be reminded, as described in the ICF to notify site personnel of any AEs occurring from the time the subject signed the ICF until the final follow-up visit. Any AEs that are ongoing at the time of the final protocol-defined study visit will be followed until the condition returns to pre-study status, has resolved or stabilized, or can be explained as being unrelated to the study drug. If a follow-up visit is deemed necessary for appropriate safety surveillance, it will take place within 30 days of the final protocol-defined study visit.

4.1 Adverse events

An AE is any untoward medical occurrence in a patient or clinical trial subject administered a pharmaceutical product and which does not necessarily have a causal relationship with this treatment.

An AE can therefore be any unfavorable and unintended sign (including an abnormal laboratory finding, for example), symptom, or disease temporally associated with the use of a product, whether or not considered related to the product. The definition of an AE includes:

- Worsening of a pre-existing condition or underlying disease
- Events associated with the discontinuation of the use of a product(s), (e.g., appearance of new symptoms)

Please note hospital admissions and/or medical/surgical procedures scheduled prior to consenting, but occurring during the study will not be captured as AEs, but will be listed in the medical history if related to a pre-existing condition. AEs or abnormal test findings will be followed until the event (or its sequelae) or the abnormal test finding resolves or stabilizes at a level acceptable to the sponsor/investigator.

4.2 Causality assessment

For each AE, the investigator will provide an assessment of causal relationship to the study drug. The causality assessment will be recorded on the appropriate AE reporting page of the subject's CRF. Causal relationship will be assessed by answering the following question:

Is there a reasonable possibility the study drug caused the event?

Yes: There is evidence to suggest a causal relationship between the study drug and adverse event; i.e.:

- There is a reasonable temporal relationship between the study drug and the event, and/or
- The event is unlikely to be attributed to underlying/concurrent disease, other study drugs, or other factors, and/or
- Positive dechallenge and/or rechallenge exist

No: There is no evidence to suggest a causal relationship between the study drug and adverse event, i.e.:

- There is no reasonable temporal relationship between the study drug and the event, or
- The subject did not take the study drug, or
- The event is likely to be attributed to underlying/concurrent disease, other study drugs, or other factors, or
- The event is commonly occurring in the (study) population independent of study drug exposure

4.3 Severity assessment

The investigator will provide an assessment of the severity of each AE by recording a severity rating on the appropriate AE reporting page of the subject's CRF. *Severity*, which is a description of the intensity of manifestation of the AE, is distinct from *seriousness*, which

implies a subject outcome or AE-required treatment measure associated with a threat to life or functionality. Severity will be assessed according to the following scale:

Mild: Minor awareness of signs or symptoms that are easily tolerated without specific medical intervention

Moderate: Discomfort that interferes with usual activities and may require minimal intervention

Severe: Significant signs or symptoms that are incapacitating with an inability to work or perform routine activities and/or that require medical intervention

